6.4. Change in the Study Design and Its Effect on the Statistical Analysis

Protocol version 1.0 (dated 28 July 2020) specified sensory function assessment by light touch. Six subjects enrolled under this version. Protocol Amendment 1 (dated 6 November 2020) adds cold sensation in the sensory function assessment. As such, six (6) subjects enrolled under Protocol v1.0 did not have cold sensation assessment. These 6 subjects will be excluded from the sensory block evaluation.

8. STUDY ENDPOINTS

8.1. Efficacy Endpoints

8.1.1. Primary Endpoint

The primary endpoint is the area under the curve (AUC) of the NRS pain intensity scores from 0 to 96 hours post-surgery comparing EXPAREL to 0.25% bupivacaine HCl.

8.1.2. Secondary Endpoints

- 1. Total postsurgical opioid consumption in oral morphine equivalents from 0 to 96 hours postsurgery comparing EXPAREL to 0.25% bupivacaine HCl
- 2. Time to first postsurgical opioid consumption comparing EXPAREL to 0.25% bupivacaine HCl
- 3. AUC of the NRS pain intensity scores from 0 to 96 hours post-surgery comparing EXPAREL to EXPAREL admixed with 0.25% bupivacaine HCl
- 4. Duration of the motor block comparing EXPAREL to EXPAREL admixed with 0.25% bupivacaine HCl (Cohort 1 only)
- 5. Proportion of opioid-free subjects through 24, 48, 72, and 96 hours from end of surgery

8.1.3. Exploratory Endpoints

- 1. Subject satisfaction as measured by International Pain Outcome (IPO) at 96 hours
- 2. AUC of "average" pain scores from POD1 through POD4 and POD1 through POD14
- 3. AUC of "worst" pain scores from POD1 through POD4 and POD1 through POD14
- 4. Current pain intensity scores post-surgery through 96 hours

8.2. Safety Endpoints

Safety endpoints will include the incidence of treatment-emergent AEs and SAEs from the start of block procedure through POD14.

8.3. Pharmacokinetic (PK) Endpoints (Cohort 1 only)

The following model-predicted PK endpoints will be determined.

- Area under the plasma concentration-versus-time curve (AUC). Specifically AUC_{0-last} and AUC_{0-∞}
- Maximum plasma concentration (C_{max}) and time of C_{max} (T_{max}). Specifically Early and Late C_{max} and T_{max}
- The apparent terminal elimination half-life $(t_{1/2})$
- Apparent clearance (CL/F)
- Apparent volume of distribution (V_{d/F})

8.4. Pharmacodynamic (PD) Endpoints (Cohort 1 only)

• Time to onset of sensory block and motor block

• Duration of the sensory block and motor block

9. METHODS OF STATISTICAL ANALYSIS

9.1. General Principles

The statistical analyses will be reported using summary tables, listings, and figures (TLFs). All analyses and tabulations will be performed using SAS[®] Version 9.4 or later. Continuous variables will be summarized using descriptive statistics [sample size (n), mean, standard deviation (SD), minimum, median, and maximum]. Categorical variables will be tabulated with number and percentage of unique subjects. Unless otherwise noted, percentages will be calculated using the number of subjects in the respective treatment group and analysis set as the denominator and presented with only those categories appearing in the data.

Individual subject data will be provided in listings. All listings will be sorted by treatment, site, subject, and, if applicable, collection date and time.

The statistical methods presented in this document supersedes the statistical analysis methods described in the clinical protocol. Significant deviations/changes from the planned analyses described in this SAP will be identified, with justification, in the appropriate section of the clinical study report (CSR).

9.2. Handling Missing Values

9.2.1. Total Post-Surgical Opioid Consumption

For the calculation of the total postsurgical opioid consumption 0-96 hours, both opioid pain medication before hospital discharge and opioid pain medication in the daily diary after discharge will be included. If opioid is taken on the start of study drug administration day but time is missing, time will be imputed as end time of surgery plus (+1) 1 minute. If opioid is taken after the day of study drug administration and time is missing, it will be imputed as 00:00.

For the calculation of the total dose through 96 hours, if a subject's last follow-up time is 96-x hours, then the opioid that was taken between 96-2x hour to 96-x hour will be used to project the amount from the last follow-up time to 96 hours, where time of last follow-up will be defined as the latter of (1) the last NRS pain assessment, (2) the start time of the last opioid pain medication, (3) time of the subject completion of the 96-hour satisfaction questionnaire, and (4) time of last sensory and motor block assessment.

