11.7. Postsurgical Pain Medication for Breakthrough Pain

An unscheduled pain intensity assessment using the NRS (measured as “How much pain are you experiencing right now?”) must be completed immediately prior to administration of any breakthrough pain medication up to 96 hours post-surgery. All opioid and other analgesics (pain medications) administered post-surgery through POD 14 must be recorded.

Medications will be provided on an as needed (PRN) basis in relation to the breakthrough pain intensity. The intent is to use the guide below in a step-wise approach; acetaminophen or NSAIDs should be used for the initial treatment of post-surgical pain and escalation to opioids (and subsequent increased dose of opioids) should be implemented if the initial pain treatment (and initial opioid dose) is insufficient for pain relief. Opioids should not be the first choice for pain relief unless clinically indicated in the opinion of the investigator and should not be given on a schedule.

- For the initial treatment of post-surgical pain, subjects may receive either acetaminophen or NSAIDs without exceeding the maximum daily dose.
- If the initial pain treatment (acetaminophen or NSAIDs) is insufficient for pain relief, immediate release PO oxycodone may be administered in a stepwise approach:
 - Initial dose of 5 mg oxycodone may be offered;
 - If the initial opioid dose is insufficient for pain relief, 10 mg oxycodone may be offered.
- If a subject is unable to tolerate PO medication or the PO oxycodone pain relief is insufficient, IV morphine (initiated at 2 mg) or hydromorphone (initiated at 0.2 mg) may be administered.

Post discharge, the subject may be provided with a prescription for oxycodone 5 mg. The subject may take acetaminophen, NSAIDs, or the prescribed oxycodone and will be given instructions on which medication to take PRN based on their pain intensity.

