13.8. Health Care Facility Discharge

- Subjects in Cohort 1 and Cohort 2 will be discharged after the completion of the 168 h and 96 h assessments, respectively.
- Record date and time of health care facility discharge.
- Re-instruct on duties and responsibilities with the e-diary and for breakthrough medications.

13.9. Postsurgical Assessments from Discharge through POD 14

- Record pain intensity scores (NRS) measured as “What was your worst pain in the last 24 hours?” and “What was your average pain in the last 24 hours?” once daily at 21:00 (± 3 h) from the day after discharge (daily continuation from POD 1 to POD 14).

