	POD 7	168h	±3h	х	х		
	POD 6	144h	±3h	х			
	S OOJ	120h	±3h	Х	Х		
		96h	±3h	Х	Х		
		84h	±2h	Х	Х		
_	04)	72h	±2h	Х	Х		
tration	4 (POI	60h	±2h	х	х		
dminis	ve Day	48h	±1h	х	х		
Drug A	operati	30h	±1h	х	Х		
study]	o Post-	24h	±1h	х	Х		
Post-	tration t	12h	±30m	Х	Х		
	Adminis	8h	±30m	Х	Х		
	ly Drug .	2h	±30m	х	Х		
	y of Stud	1h	±15m	Х	Х		
	Da	45m	45m ±5m X		Х		
		30m ±5m		Х	х		
		15m	±5m		х		
		Up to 15 mins	before blocks	Х	Х		
		Time Window		Collect PK blood sample; Record date and time of blood sample	Assess and record sensory and motor function ^{b,c}		

Table 2: Pharmacokinetic and Pharmacodynamic Assessment Schedule (Cohort 1 bunionectomy subjects only)

Abbreviations: h=hour; m=minute; PK=pharmacokinetic

a. All timepoints are from end of block administration.

- Once offset of sensory and motor block are determined (in two consecutive evaluations), no subsequent assessments will be conducted. Sensory and motor are assessed independently م
- When subject is in surgery, no sensory or motor block assessments be conducted.

5. **DEFINITIONS**

Start and End of Block

See Sections 6.3.1 and 6.3.2 for onset and offset of sensory block and motor block, respectively.

Study Day

Study Day is calculated as the date of event minus the date of end of study drug administration plus one (1), if the date of event is on or after the date of end of study drug administration. If the date of event is before the end of study drug administration, study day is the date of event minus the date of study drug administration.

Time 0

For PK, PD, and safety evaluation, Time 0 is defined as the date and time of the end of the study drug administration. For NRS pain collection and opioid consumption, Time 0 is defined as the date and time of the end of the surgery.

Baseline

Baseline is defined as the last available measurement prior to start of study drug administration.

Surgical Type

It is expected this study will enroll patients for bunionectomy, 1st metatarsophalangeal fusion, specific forefoot surgeries, midfoot fusion, hindfoot fusion, and total ankle arthroplasty. Due to overwhelmingly large number of bunionectomy patients enrolled as of this date, patients will be subgrouped into bunionectomy and non-bunionectomy for the purpose of by-subgroup summaries.

Treatment-Emergent Adverse Events (TEAEs)

TEAEs are those with onset date and time on or after the start date and time of study drug administration.

Beginning of Surgery

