9.2.5. Time to Event

For calculating time to an event when only the hour is reported, the minutes will be set to zero. The censoring method is described in Sections 6.3.1 and 6.3.2 when the onset time or the offset time of sensory or motor block is not captured.

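### Two SAP time-imputation rules lack a bound: an untimed POD 4 opioid dose always counts in 0-96 h, even after a later discharge, and an hour-only time can precede Time 0

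*SAP*

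**What the plan says.** **Untimed opioid doses.** SAP 9.2.1 covers the 0-96 h total and draws on two sources: "both opioid pain medication before hospital discharge and opioid pain medication in the daily diary after discharge will be included". For a dose without a time on the dosing day, "time will be imputed as end time of surgery plus (+1) 1 minute". For later days, "If opioid is taken after the day of study drug administration and time is missing, it will be imputed as 00:00". The section refers neither to the recorded discharge time nor to hour 96 when it places the dose.

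**Hour-only times.** SAP 9.2.5 has one rule: "For calculating time to an event when only the hour is reported, the minutes will be set to zero". It gives no lower limit. SAP 9.5.2.2 then takes the first opioid time minus the end of surgery, also without a floor.

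**Time 0.** The Time 0 definitions in SAP Section 5 use full date and time. For opioids: "For NRS pain collection and opioid consumption, Time 0 is defined as the date and time of the end of the surgery". For block onset: "For PK, PD, and safety evaluation, Time 0 is defined as the date and time of the end of the study drug administration".

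**Discharge.** Protocol 13.8: "Subjects in Cohort 1 and Cohort 2 will be discharged after the completion of the 168 h and 96 h assessments, respectively". The same section has the site record the date and time of discharge. Planned discharge on POD 4 therefore concerns Cohort 2.

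**The concern.** Each rule can contradict a time that is already in the database.

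Under 9.2.1, a diary dose taken at home on POD 4 is moved back to midnight, when the subject was still in the facility. If discharge was after hour 96, the dose is known to lie outside the endpoint's window, yet it is summed. This affects total OMED 0-96 h, the first secondary endpoint and the second step of the testing hierarchy in SAP 9.5. If the same imputed time is used for opioid-free status through 96 h (fifth in the list in SAP 8.1.2), the subject also loses that status.

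Under 9.2.5, an event in the same clock hour as Time 0 gets a time of zero or less. A negative time cannot enter a Kaplan-Meier analysis. If postsurgical status is judged on the truncated time, the dose counts as presurgical and a later dose becomes the first. Either way, the second secondary endpoint (time to first opioid) is wrong for that subject. Time to block onset, measured from the end of study drug administration, is exposed in the same way.

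**Working it through.** The plan gives no figure for either rule, so there is none to reproduce. The check is clock arithmetic on the rules as written.

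**Inputs**
- Untimed dose after the dosing day: 00:00 of its date (SAP 9.2.1).
- Opioid Time 0: end of surgery, at clock time T (SAP Section 5). Dosing and surgery fall on the same day (Protocol 9.2).
- Oxycodone PO factor 1.5 (SAP Table 5); 5 mg prescribed after discharge (Protocol 11.7).
- Value assigned to a subject with no opioid: 3.75 mg OMED, analysed on the log scale (SAP 9.5.2.1).
- 40 subjects per arm (SAP Section 10).
- T is not in the documents. 09:00 to 16:00 is my assumption for illustration.

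**1. Where an untimed POD 4 dose lands**

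Hour 96 is clock time T on POD 4, so 00:00 on POD 4 is 96 - T hours. The part of POD 4 that lies after hour 96 is (24 - T)/24.

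| End of surgery | 00:00 on POD 4 | Part of POD 4 after hour 96 |
|---|---|---|
| 09:00 | 87 h | 62.5% |
| 12:00 | 84 h | 50% |
| 16:00 | 80 h | 33% |

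For every T from 00:01 to 23:59 the imputed time lies between 72 and 96 h, so the dose is always counted. On POD 5, 00:00 is 120 - T, which is always beyond 96 h. The problem is therefore confined to POD 4.

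Example: surgery ends at 09:00 and discharge is at 11:00 on POD 4, which is 87 + 11 = 98 h. Any dose after discharge is at 98 h or later, but an untimed one is placed at 87 h and summed. In the extreme, a dose at 23:59 (about 111 h) is counted at 87 h.

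**2. Size for one record**
- 5 mg x 1.5 = 7.5 mg OMED.
- Otherwise opioid-free subject: 7.5 / 3.75 = 2, so the analysed value doubles.
- Effect on the geometric mean of a 40-subject arm: exp(ln 2 / 40) - 1 = exp(0.0173) - 1 = about 1.7%.
- Subject with x mg of other opioid: the ratio is (x + 7.5)/x, which approaches 1 as x grows. The opioid-free case is therefore the sensitive one.

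**3. Hour-only times**

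If Time 0 is m minutes past the hour and the event is in the same clock hour, the derived time is -m minutes, anywhere from 0 to -59. With surgery ending at 10:40 and an opioid at hour 10: 10:00 - 10:40 = -40 min = -0.67 h.

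**4. Does another section guard against this?**

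No other section does so for these two cases. The SAP does anchor to a recorded time elsewhere: end of surgery + 1 minute for dosing-day opioids (9.2.1), and the time of study treatment for adverse events on the dosing date (9.2.3).

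**The case against.** The strongest reply is that the trigger may hardly ever occur. Protocol 13.1 has data through the primary endpoint collected under staff supervision, Protocol 13.6 asks for the date, time and dosage of breakthrough medication in the PACU, and the eCRF may not accept a missing time. The rules are the same in all arms, and 00:00 never drops a POD 4 dose that truly belongs in the window. All of this stands and limits the size. It does not make an out-of-window dose or a negative time correct.

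Four stronger readings are tempting, and the documents do not support them.

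- *All post-discharge POD 4 doses are miscounted.* The 96 h assessment has a window of ±3 h, so discharge from about 93 h is possible and a dose soon after it may be in the window. The error is certain only when discharge was after hour 96. An untimed Cohort 1 inpatient dose on POD 4 is not known to be outside either.
- *Shifts of up to a day on POD 1 to 3 distort the total.* The endpoint is a sum, and those doses lie inside 0-96 h at any clock time. Only the projection for subjects whose follow-up ends early could be touched.
- *The primary AUC is affected.* SAP 9.2.2 does not say that imputed opioid times open the worst-observation windows. This is an open question, not an established consequence.
- *Block onset is widely corrupted.* That would need hour-only records for staff-performed assessments with windows of ±5 to ±15 min. SAP 6.3 also describes a dedicated eCRF page for onset and offset times.

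A reader might also want to recover the dose time from the pre-dose pain score, which "must be completed immediately prior to administration of any breakthrough pain medication up to 96 hours post-surgery". That score also precedes acetaminophen and NSAIDs, so it need not belong to the untimed opioid.

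**Conclusion.** The point holds as a minor defect in two stated rules. As written, SAP 9.2.1 always counts an untimed POD 4 dose in 0-96 h, including a diary dose that a recorded discharge after 96 h shows to be outside. SAP 9.2.5 can produce a zero or negative time to event.

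Per record, the first can double the analysed OMED of an otherwise opioid-free subject (about 1.7% on the geometric mean of an arm of 40). The second can lose or misplace a first opioid or a block onset. The direction of any net effect between arms cannot be told from the documents.

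The conclusion rests on the rules being programmed literally. The frequency of untimed or hour-only records is not given and is probably low, so the expected effect on the trial is small and mainly on secondary and pharmacodynamic endpoints. The effect on opioid-free status applies only if the imputed times are used there, which the SAP does not state.

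**What to change.** Before unblinding, make three short changes.

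1. **SAP 9.2.1.** Set an untimed post-discharge diary dose on the day of discharge no earlier than the recorded discharge time. It is then excluded from 0-96 h only if discharge was after 96 h. With surgery ending at 09:00, discharge at 11:00 on POD 4 (98 h) excludes the dose, and discharge at 07:00 (87 + 7 = 94 h) keeps it. Leave 00:00 for all other untimed doses after the dosing day.
2. **SAP 9.2.5.** For an event known to follow Time 0 with only the hour recorded, use the later of hour:00 and Time 0 + 1 minute. Time 0 is the end of surgery for opioids and the end of study drug administration for block onset. This extends the convention that 9.2.1 already uses on the dosing day.
3. **Scope.** State whether the imputed opioid times also apply to time to first opioid, opioid-free status and the worst-observation windows of SAP 9.2.2.

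The cost is two or three sentences and minor programming. Discharge, end of surgery and end of block are already recorded under Protocol 12.1 and 13.8, so no new data are needed.

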11.3.3. Replacement of Subjects

Subjects who withdraw from the study before receiving study drug may be replaced. Once a subject number is assigned, subject numbers will not be reused; subjects enrolled to replace those who withdraw will be assigned a unique subject number and randomized to treatment according to the procedures outlined above. Subjects who are randomized but are withdrawn from the study before receiving study drug or do not undergo the surgical procedure may be replaced. Additionally, subjects may be replaced if insufficient and/or incomplete data are noted on PK profiles or efficacy endpoints.

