15.4. Analysis Populations

The following analysis sets are planned:

Safety: The safety analysis set will include all subjects who receive study drug. All analyses will be based on actual treatment received.

Efficacy: The efficacy analysis set will include all randomized subjects who undergo the planned surgery. All analyses will be based on randomized treatment regardless of actual treatment received.

Pharmacokinetic: The pharmacokinetic analysis set will include all subjects who receive study drug and who provide sufficient samples to allow for calculation of PK parameters required for analysis.

Pharmacodynamic: The pharmacodynamics analysis set will include all subjects who receive study drug and who provide sufficient data to allow for calculation of PD parameters required for analysis.

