9.5. Efficacy Analysis

For Primary and Secondary Efficacy Analyses, descriptive statistics that are appropriate for the efficacy variable will also be shown by surgical type, but no statistical analyses will be performed within a surgery type. All efficacy analyses will be performed using the Efficacy analysis set.

Unless specified otherwise, all confidence interval will be 2-sided with 95% confidence. All statistical comparison will be 2-sided at alpha=0.05 level. The leading statistical comparison is between EXPAREL and 0.25% bupivacaine HCl for the primary and first two secondary endpoints and between EXPAREL and EXPAREL admixed with 0.25% bupivacaine HCl for the third and fourth secondary endpoints, though all 3 pairwise comparisons (EXPAREL vs 0.25% bupivacaine HCl, EXPAREL vs EXPAREL admixed with 0.25% bupivacaine HCl, and EXPAREL admixed with 0.25% bupivacaine HCl, and EXPAREL admixed with 0.25% bupivacaine HCl, will be presented.

To control for the overall Type-I error rate for the multiple comparisons, the statistical tests will be conducted in the hierarchical order as follows. See also Section 8.1 for detail.

- 1. Primary endpoint: EXPAREL vs 0.25% bupivacaine HCl
- 2. First secondary endpoint: EXPAREL vs 0.25% bupivacaine HCl
- 3. Second secondary endpoint: EXPAREL vs 0.25% bupivacaine HCl
- 4. Third secondary endpoint: EXPAREL vs EXPAREL admixed with 0.25% bupivacaine HCl

5. Fourth secondary endpoint: EXPAREL vs EXPAREL admixed with 0.25% bupivacaine HCl

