9.5.2. Secondary Efficacy Endpoints

9.5.2.1. Total postsurgical opioid consumption in oral morphine equivalents from 0 to 96 hours post-surgery comparing EXPAREL to 0.25% bupivacaine HCl

Total postsurgical opioid consumption (OMED mg) will be summarized by treatment group and surgery type using Efficacy Analysis Set. The summary will include number of subjects receiving postsurgical opioids, geometric mean and coefficient of variation (CV%), median, minimum and maximum.

To test for significant difference between EXPAREL and 0.25% bupivacaine HCl, an analysis of covariance (ANCOVA) model with treatment as main effect and investigator site (categorical), age, and height as covariates will be applied to the natural log-transformed total dose. The LS means for EXPAREL and 0.25% bupivacaine HCl, LS mean difference between

EXPAREL and 0.25% bupivacaine HCl, two-sided 95% CI for the LS mean difference, and the two-sided p-value will be reported after back transformation (ie, taking exponential) to the original OMED scale. If a subject does not have postsurgical opioid consumption, a 3.75 mg OMED will be assigned for the ANCOVA analysis using log-transformation.

In addition to the presentation for the between group difference, the percent reduction in total opioid consumption will also be presented similar to Section 9.5.1.

As sensitivity analysis, this endpoint will also be analyzed using the non-stratified Cochran-Mantel-Haenszel test for the row mean score difference with modified ridit scores.

A sample SAS code is as follows.

```
PROC FREQ ;
    TABLES trtp*omed / CMH SCORE=modridit ;
RUN ;
```

Another sensitivity analysis will be carried out in the same way as for the primary analysis using ANCOVA but excluding two subjects described in Section 9.5.1.

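### The rule that projects opioid use to 96 h looks back past the end of surgery when last follow-up is before 48 h, and the SAP does not say how to handle that case

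*SAP*

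**What the plan says.** SAP 9.2.1 covers incomplete follow-up for total opioid consumption. It begins "if a subject's last follow-up time is 96-x hours" and continues that "the opioid that was taken between 96-2x hour to 96-x hour will be used to project the amount from the last follow-up time" to 96 h. Last follow-up is the latest of four events: the last NRS score, the start of the last opioid dose, the 96-hour satisfaction questionnaire, and the last sensory and motor assessment.

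SAP Section 5 fixes the origin: "For NRS pain collection and opioid consumption, Time 0 is defined as the date and time of the end of the surgery".

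The endpoint is second in the test hierarchy of SAP 9.5 ("First secondary endpoint: EXPAREL vs 0.25% bupivacaine HCl"). SAP 9.5.2.1 analyses it by ANCOVA on the natural log of total dose. For non-users: "If a subject does not have postsurgical opioid consumption, a 3.75 mg OMED will be assigned for the ANCOVA analysis using log-transformation".

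Early dropouts stay in the analysis. Protocol 15.4 says "The efficacy analysis set will include all randomized subjects who undergo the planned surgery". Protocol 11.3.3 says "subjects may be replaced if insufficient and/or incomplete data are noted on PK profiles or efficacy endpoints", which adds subjects but does not take the dropout out of the efficacy set.

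**The concern.** The rule covers x unobserved hours with the x hours observed just before them. That works only if x observed postsurgical hours exist. When follow-up ends before 48 h the window reaches back before the end of surgery, where no postsurgical dose can lie. A shorter observed period then has to stand for a longer unobserved one, and the SAP does not say how.

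Two things are at stake. The total could be too low for the subjects who leave earliest, on an endpoint that carries a formal test. And two programmers could follow the same sentence and obtain totals that differ by a factor of two to four for the same subject, with the choice made after data are in hand.

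**Working it through.** The documents give no figure for this rule, so there is none to reproduce. The check is arithmetic on the rule.

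**Inputs**
- T = last follow-up in hours after the end of surgery; x = 96 − T (SAP 9.2.1).
- Look-back window: from 96 − 2x to 96 − x, a length of x hours (SAP 9.2.1).
- Time 0 = end of surgery (SAP Section 5).
- 40 subjects per arm (Protocol 15.3, SAP Section 10); log-scale analysis (SAP 9.5.2.1).
- Assumption: constant hourly use r after surgery.
- Reading: the window amount is carried over one for one, since window and gap have the same nominal length.

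**Step 1. When the window leaves the postsurgical period.** 96 − 2x < 0 exactly when x > 48, that is, T < 48 h.

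**Step 2. Total under the rule.** Observed use is rT. The window holds r × min(x, T).
- T ≥ 48 h: total = rT + r(96 − T) = 96r. The rule reproduces the constant-rate total.
- T < 48 h: total = rT + rT = 2rT. As a fraction of 96r this is 2T/96.

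| T (h) | x (h) | Window start (h) | Rule total | Fraction of 96r | ln fraction |
|---|---|---|---|---|---|
| 60 | 36 | 24 | 96r | 1.00 | 0 |
| 48 | 48 | 0 | 96r | 1.00 | 0 |
| 42 | 54 | −12 | 84r | 0.875 | −0.13 |
| 36 | 60 | −24 | 72r | 0.75 | −0.29 |
| 24 | 72 | −48 | 48r | 0.50 | −0.69 |
| 12 | 84 | −72 | 24r | 0.25 | −1.39 |
| 6 | 90 | −84 | 12r | 0.125 | −2.08 |

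Example: 30 mg OMED in 24 h, then lost. The rule gives 30 + 30 = 60 mg. The constant-rate total is 30 × 96/24 = 120 mg.

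**Step 3. Effect on the arm.** One subject in 40 moves the arm's log mean by 0.69/40 = 0.017 (T = 24 h) or 1.39/40 = 0.035 (T = 12 h). The arm's geometric mean falls by 1.7% or 3.4%.

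**Step 4. A literal negative window.** Protocol 11.6.2 permits intraoperative fentanyl up to 1 µg/kg, or more if medically necessary. SAP Table 5 converts fentanyl at 300 per mg. At an assumed 60 to 100 kg this is 0.06 to 0.10 mg × 300 = 18 to 30 mg OMED, which could offset or reverse the shortfall in Step 2.

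**Step 5. The alternative.** Let A be the OMED taken between max(0, 96 − 2x) and 96 − x. Projected amount = x × A / (96 − x − max(0, 96 − 2x)).
- T ≥ 48 h: the divisor is x, so the projected amount is A, as now.
- T < 48 h: the divisor is T, so the total is A × 96/T, which equals 96r at a constant rate.
- With very short follow-up the multiplier is large: 15 mg OMED with T = 6 h becomes 15 × 96/6 = 240 mg, against 30 mg by one-for-one carry-over. The formula needs a guard.

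**The case against.** The case against giving this weight has several parts.

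**The carry-over is inferred.** A reader might conclude that following the SAP exactly makes the total too low by a known factor. The text does not support that. It says the window opioid is used to project; it does not say the amount is added unchanged. A programmer who divided by the hours observed after surgery would remove the shortfall. This stands: one-for-one is the natural reading, not a stated formula, and the firm finding is that the SAP leaves T < 48 h undefined.

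**The size and direction are not fixed.** The fractions need a constant rate. Protocol 7.3 says plain bupivacaine usually acts for less than 8 hours and EXPAREL releases slowly, so use may change over time and differently by arm. Intraoperative fentanyl could push the other way. A subject who used no opioid is unaffected: any version projects zero, and 3.75 mg is then assigned. All this stands. The constant rate is still a fair benchmark, because it is the one under which the rule is exact when T is 48 h or more.

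**Few subjects can be affected.** Protocol 13.8 says "Subjects in Cohort 1 and Cohort 2 will be discharged after the completion of the 168 h and 96 h assessments, respectively". All four sources of last follow-up must end before 48 h. This stands, and the documents give no dropout rate. Withdrawal is nonetheless foreseen, including for events uncovered during surgery (Protocol 10.3.1).

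**The shift is small.** The documents give no SD for log OMED. At an assumed 1.0 to 1.5, the standard error of the difference is SD × √(2/40) = 0.22 to 0.34, so one subject moves the estimate by about 5% (0.017/0.34) to 16% (0.035/0.22) of one standard error. The rank-based sensitivity analysis in SAP 9.5.2.1 also limits the pull of single values. Both points stand.

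**Conclusion.** The gap is real and the 48 h threshold is exact. SAP 9.2.1 gives no usable instruction for a subject last seen before 48 h, and no other section repairs it. Under one-for-one carry-over and a constant rate, such a subject receives 2T/96 of the 0 to 96 h total: 75%, 50% and 25% at 36, 24 and 12 h. For T of 48 h or more the rule is sound.

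A reader might infer that the first secondary endpoint is biased. The documents do not show that. It would take early exits among opioid users that differ by arm, and nothing in the documents indicates how many there will be or in which arm. The expected effect is small, at 0.017 to 0.035 on an arm's log mean per affected subject last seen at 24 or 12 h. The reason to act is that the rule exists for incomplete follow-up, fails for the most incomplete cases, and can be settled cheaply while treatment is still blinded.

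**What to change.** Amend SAP 9.2.1 before unblinding:

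1. Truncate the look-back window at Time 0 and count postsurgical opioid only.
2. State the formula: projected amount = x × (OMED taken between max(0, 96 − 2x) and 96 − x) / (96 − x − max(0, 96 − 2x)).
3. Prespecify a minimum observed period below which the subject's own rate is not extrapolated. For example, impute from the observed data of that treatment arm instead.
4. Add a sensitivity analysis that varies the handling of subjects with T under 48 h.

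The formula itself costs one sentence and one line of code. The guard and the sensitivity analysis add a little more text and programming. Every subject followed to 48 h or later keeps the same value as now. The downside is slightly more variable totals for the few early dropouts, which the minimum period is there to limit.
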